Appendix A Visual Analog Scale

1. Background

Corticosteroid therapy, including intralesional and topical applications, has many indications within the fields of Dermatology, Plastic Surgery, and Orthopedics. However, these injections can be quite painful, which leads many patients to discontinue treatment.

Often, the injection involves a mixture of local anesthetic and corticosteroids despite a lack of evidence that the use of lidocaine improves pain.^{1,2} Due to the acidic pH, the lidocaine component of the injection can actually cause a significant burning sensation during the procedure. Lidocaine does not have anti-inflammatory properties and does not treat the underlying pathology. By including another medication, lidocaine also adds cost and risk to the procedure.

In a double blind, randomized control trial, Osanakornkul and Burusapat studied the benefit of applying topical anesthetics or a 1:1 mixture of 1% lidocaine and triamcinolone acetonide at the injection site to alleviate pain during keloid treatment.² While the use of a topical anesthetic 1 hour prior to the injection was able to alleviate the pain from needle stick, the study did not show a statistical difference in pain outcomes with the use of lidocaine. However, this study was limited to the use of intralesional corticosteroid injections for the treatment of keloids. In addition, the study only focused on 3 locations: the shoulder, sternum, and ear. Keloid injections are often more painful than other injections because the horizontal penetration of the needle can pierce a large number of nerve endings. In routine injections, the entry of the needle is either vertical or angled and thus pierces a small number of nerve endings.³ In addition, the injected material stretches nerve endings and compresses them against unyielding keloid tissue, causing substantial pain that can persist up to several hours after the procedure.³ This study will examine intralesional corticosteroid injections for keloids, alopecia areata, and other indications while including a wider variety of injection sites.

2. Rationale and Specific Aims

The purpose of this study is to see if removing lidocaine from intralesional injections decreases pain of the injection. We hypothesize there will be no difference in pain outcomes if lidocaine is removed from intralesional corticosteroid injections.

3. Animal Studies and Previous Human Studies

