A similar study was conducted in plastic surgery with intraarticular injections for trigger finger. The project examined pain outcomes for injections containing steroid + normal saline vs steroid + local anesthetic. The results indicated that injections containing local anesthetic were significantly more painful. Thus, including a mixed local anesthetic in the injection adds unnecessary cost and risk to the procedure. Because steroid injections in dermatology are also commonly mixed with a local anesthetic, this study design can be applied to these intralesional injections as well.

4. Inclusion/Exclusion Criteria

Inclusion Criteria:

- >12 years old presenting with an indication for intralesional steroid injection

Exclusion Criteria:

- Not a candidate for corticosteroid injection
- Contraindication to lidocaine

5. Enrollment/Randomization

All patients meeting inclusion/exclusion criteria will be offered enrollment. Using a coin flip, patients will have a 50% chance of receiving one of the following treatments:

1. Corticosteroid + lidocaine
2. Corticosteroid + normal saline

6. Study Procedures

Day 1 (In clinic): After diagnosing the need for an intralesional injection, patients will be screened for enrollment. The consent form will be reviewed in depth to describe the purpose and procedures associated with the study. If they agree to be part of the study, we will collect the following demographic information:

- MRN
- Age
- Gender
- Comorbidities (chronic opioid use, smoking, diabetes, neuropathy, fibromyalgia)
- Phone number
- Site of injection (scalp, face, neck, and trunk)
- Indication for injection

The patient will then be randomized to receive one of the following injections:

1. Corticosteroid with normal saline
2. Corticosteroid with lidocaine

A co-investigator will prepare the syringe to ensure blinding. The injection site will be prepped in sterile fashion with an alcohol wipe. The physician will then administer the injection. Immediately following the injection, the patient will be asked to rate the pain of the injection based on the visual analog scale (appendix A). Specifically, the co-investigator will say "Rate the injection experience on a scale of 0 to 10, 0 being no pain and 10 being the worst pain of your life". A bandaid will be placed over the injection site and the patient will be reminded to expect a phone call that afternoon and the next day.

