Day 1 (after clinic): Approximately 6 hours after the injection, a different study investigator will call the patient by phone to assess their current pain level with the visual analog scale. Using a different investigator who is unaware of the treatment arm for follow-up will further ensure blinding. Specifically, the investigator will say "Rate your

current pain level from the injection on a scale of 0 to 10, 0 being no pain and 10 being the worst pain of your life". Patients will be called up to three times before being considered lost to follow-up.

Day 2: Approximately 24 hours after the injection, the study investigator will again call the patient by phone to assess their current pain level with the visual analog scale. Specifically, the investigator will say "Rate your current pain level from the injection on a scale of 0 to 10, 0 being no pain and 10 being the worst pain of your life". Patients will then be thanked for their involvement in the study and encouraged to reach out to the principle investigator or clinic should any problems arise. Patients will be called up to three times before being considered lost to follow-up.

7. Risks

This study is categorized as less than minimal risk. We are comparing two treatment methods that are accepted as standard of care, and are already used on the clinic population being studied on a daily basis. There is no new experimental intervention that would put patients at greater than minimal risk. Although rare, the risks of a corticosteroid injection include hypopigmentation, skin atrophy, and hyperglycemia in patients with diabetes. There is also a small risk of an allergic reaction to the lidocaine component. There may be unknown or unanticipated adverse effects.

8. Reporting of Adverse Events or Unanticipated Problems Involving Risk to Participants or Others

Adverse events will be reported to the IRB immediately through standard reporting mechanisms.

9. Study Withdrawal/Discontinuation

There are no anticipated circumstances under which subjects would be withdrawn from research without their consent. If subjects withdraw, there will be no penalty or consequences.

10. Statistical Plan

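### As worded, Section 6 lets the person who prepared the syringe ask for the immediate pain score; an asker unaware of the arm is specified only for the follow-up calls

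*Combined protocol and SAP*

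**What the plan says.** Section 6 of the combined protocol and SAP describes the clinic visit in sequence. On preparation: "A co-investigator will prepare the syringe to ensure blinding". On administration: "The physician will then administer the injection". Straight afterwards, "the patient will be asked to rate the pain of the injection based on the visual analog scale (appendix A"), and the sentence that gives the prompt begins "Specifically, the co-investigator will say". No other co-investigator appears between the first mention and the second.

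For the call at about 6 hours, Section 6 says that "a different study investigator will call the patient by phone to assess their current pain level with the visual analog scale", and gives the reason: "Using a different investigator who is unaware of the treatment arm for follow-up will further ensure blinding". At about 24 hours the study investigator telephones again.

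Section 2 gives the aim, "The purpose of this study is to see if removing lidocaine from intralesional injections decreases pain of the injection", and the expectation, "We hypothesize there will be no difference in pain outcomes if lidocaine is removed from intralesional corticosteroid injections". No section names a primary time point.

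**The concern.** Having someone other than the physician prepare the syringe protects blinding because that person holds the knowledge of the arm and others do not. If the same person then asks the patient for the score, the knowledge comes back at the moment of measurement. Section 6 describes no coded vials, pharmacy preparation or other step that would keep the preparer unaware.

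At stake is the immediate rating. It is the only one taken at the procedure, and its script asks about the experience of being injected. An asker who knows the arm could, without meaning to, vary tone or follow-up remarks, or settle a hesitant answer differently, according to arm. Nothing in the data that Section 6 plans to collect would show this afterwards, so it is better prevented in the procedure.

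**Working it through.** The point involves no calculated figure in the plan. The only computed design figure, the sample size in Section 10, does reproduce: with a difference of 0.2, an SD of 0.3, two-sided 0.05, and 34 and 39 subjects, a two-sample t-test has power 0.800. It is tied to no time point, and nothing below depends on it.

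The check is a reading of who does what, all from Section 6:

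| Rating | Who asks | Stated to be unaware of the arm? | What the script asks about |
|---|---|---|---|
| Immediate, in clinic | The co-investigator | No statement | The experience of the injection |
| About 6 h, by phone | A different study investigator | Yes | Pain from the injection felt at that time |
| About 24 h, by phone | The study investigator, again | Yes, if this is the same caller (assumed) | Pain from the injection felt at that time |

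1. **Are preparer and asker the same person?** The first mention has the indefinite article and the second the definite article, with only the physician in between. The natural reading is one person. This is an inference.
2. **Does that person know the arm?** This is also inferred: they prepare a syringe containing either lidocaine or saline, and no masking of the preparer is described. Section 5 assigns treatment by coin flip without saying who learns the result.
3. **Does the text on follow-up help?** It can be read two ways. The words for different and unaware suggest that the clinic asker is aware. The claim to strengthen blinding further suggests that the drafters thought the clinic stage was already blinded. On neither reading is the person asking in clinic said to be unaware.
4. **Count.** Planned ratings: 3. With an unaware asker stated: 2. Without: 3 − 2 = 1. Ratings whose script asks about the experience of the injection: 1, the same one.
5. **Direction of any bias.** Section 2 expects no difference between arms, whereas Section 3 reports a trigger-finger study in which the mixture with local anesthetic hurt more. An asker could hold either expectation, so no direction follows. No size follows either.

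**The case against.** The strongest reply is that the patient is the rater. The co-investigator reads a fixed prompt and the patient supplies a number, so nobody aware of the arm judges the outcome. That stands, and it limits the bias route to cueing or recording. It is also fair that the identity of preparer and asker is inferred, and that the content of Appendix A is not visible in the text reviewed. If patients mark that scale themselves, part of the remedy may already be in place.

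Three stronger readings are tempting, and the documents do not support them.

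- A reader might infer that an unblinded assessor scores the main outcome. The assessor is the patient, and no main time point is named.
- A reader might infer that only the immediate rating concerns the injection, and so that it alone answers the study question. Both phone scripts also ask about pain from the injection. They differ in asking about pain still present hours later. The hypothesis in Section 2 speaks of pain outcomes in general. The immediate score is closest to the aim, and no more than that can be said.
- A reader might reason from the planned difference of 0.2 in Section 10 that a one-point shift in one patient in five in one arm (1 × 1/5 = 0.2) would equal the whole effect. Section 10 gives no units for the 0.2, and nothing in the documents suggests that a shift of that kind would occur.

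What remains is that the procedure, followed as written, does not keep someone who knows the arm away from the immediate score, although the plan takes that care for follow-up.

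**Conclusion.** The point holds as a minor one, a cheap improvement. One of the three planned ratings, the immediate one, has no statement that the person asking is unaware of the arm, and the natural reading gives the task to the preparer of the syringe. This rests on three assumptions: that both mentions of a co-investigator refer to one person, that preparing the syringe reveals the arm, and that the 24-hour caller is the same unaware investigator as at 6 hours. If the first or second is wrong, the procedure may already be sound and only the wording needs attention. The bias route is narrow and no estimate of its effect is possible.

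**What to change.** If the person who asks in clinic is already meant to be someone else who is unaware of the arm, say so in that sentence of Section 6. Otherwise add: *Whoever prepares the syringe or knows the allocation will not ask for or record the immediate score.* Then name one of two routes:

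- the patient marks the Appendix A scale without the preparer's involvement (if patients already mark it, state only that the preparer takes no part); or
- someone already present who is stated to be unaware of the arm asks with the same script. This could be the injecting physician, provided the protocol states that the physician is blinded, which it now only implies.

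The cost is one or two sentences. Both routes can use a tool or person already named in Section 6, and the sample size does not change. The downsides are small: a marked scale differs in mode from the spoken phone ratings, and a patient may be more reserved with the physician who gave the injection. Either would apply equally to both arms.

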We are planning a study of a continuous response variable from independent control and experimental subjects with 1.1538 control(s) per experimental subject. In a previous study the response within each subject group was normally distributed with standard deviation 0.3. If the true difference in the experimental and control means is 0.2, we will need to study 34 experimental subjects and 39 control subjects to be able to reject the null hypothesis that the population means of the experimental and control groups are equal with probability (power) 0.8. The Type I error probability associated with this test of this null hypothesis is 0.05.

11. Privacy/Confidentiality Issues

Private health information (PHI) will be used in the study, but not disclosed. All PHI will be stored on a secure, password-locked server. All participants in the study have obtained Human Research certification to have the necessary authorization to PHI. When collecting patient data, only medical record numbers will be used to identify patients.

[figure not shown]
12. Follow-up and Record Retention

The study will last for approximately 1 year after initiation or until the enrollment goal is met. At the study conclusion, all identifiable data will be destroyed and de-identified data will be kept for analysis.

13. References:

2. Usanakornkul, A., & Burusapat, C. (2017). A Topical Anesthetic and Lidocaine Mixture for Pain Relief During Keloid Treatment. *Dermatologic Surgery*, 43(1), 66-73. doi:10.1097/dss.0000000000000932
3. Mishra S Safe and less painful injection of triamcinolone acetonide into a keloid—a technique. *J Plast Reconstr Aesthet Surg* 63:e205

Appendices:

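### Missed phone ratings: it is unclear whether a patient missed at 6 h is still called at 24 h, and comparing only answered ratings can bias the 6 h and 24 h results if answering depends on immediate pain

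*Combined protocol and SAP*

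**What the plan says.** The combined protocol and SAP, Section 6, plans three ratings per patient: one in clinic straight after the injection, one by phone at about 6 h (Day 1, after clinic) and one by phone at about 24 h (Day 2). The 6 h paragraph ends with "Patients will be called up to three times before being considered lost to follow-up". The Day 2 paragraph says that "the study investigator will again call the patient by phone", and then repeats the same three-call sentence. Before leaving the clinic, patients are told to expect both calls.

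Section 10 is a sample-size paragraph for one unnamed continuous response. Its test would "reject the null hypothesis that the population means of the experimental and control groups are equal". It names no primary time point, analysis set or method for missing ratings, and makes no allowance for unreached patients. Section 2 hypothesises no difference in pain between the arms and gives no margin.

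**The concern.** There are two gaps.

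- **Follow-up.** The 6 h rule attaches the label of being lost to the patient, not to the rating. Site staff could take that as ending contact and skip the 24 h call, although the patient may be easy to reach the next day.
- **Analysis.** A comparison of two means needs a value from each patient it includes, so at 6 h and 24 h it would by default use only those who answered. That is sound if answering is unrelated to pain. If it is related, the answered patients in the two arms are selected differently whenever the arms differ in immediate pain. The protocol gives some reason to expect such a difference: Section 1 describes a burning sensation from lidocaine, and Section 3 reports that injections with local anaesthetic hurt more in a trigger-finger study.

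At stake are the 6 h and 24 h arm differences. The in-clinic rating needs no phone call, and it carries the information that could correct the later comparisons.

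**Working it through.** **1. The plan's own figure.** Inputs from Section 10: difference 0.2, SD 0.3, type I error 0.05, power 0.8, and 1.1538 controls per experimental subject. A two-sided two-sample t-test with 34 and 39 patients has power 0.800, so the stated size reproduces with no reserve. With assumed equal non-contact of 10% (31/35 rated) power is 0.76, and with 20% (27/31) it is 0.70. That is lost precision, not bias.

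**2. Assumptions for the bias check.** The documents give no non-contact rate and no link between pain and answering, so these are assumed ranges:
- immediate arm difference 0.2/0.3 = 0.667 SD, borrowed from Section 10;
- correlation r between the immediate and 6 h ratings of 0.5 to 0.7;
- 10% or 20% unreached;
- odds of not answering changing 2.7-fold or 7.4-fold per SD of immediate pain, upward or downward, alike in both arms.

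**3. Formula.** With jointly normal ratings, the bias of the answered-only 6 h difference is r × (S1 − S2). Here S1 and S2 are, for each arm, the mean immediate rating among answerers minus the mean among all patients. The true 6 h difference does not enter this expression. It decides only whether a given bias shrinks or enlarges the result.

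**4. Persisting difference.** Take the true 6 h difference as r × 0.667, that is 0.333 SD (r = 0.5) or 0.467 SD (r = 0.7). Simulation gave the following for both directions of dependence:

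| Unreached | 2.7-fold | 7.4-fold |
|---|---|---|
| 10% | about 7% too small | about 15% too small |
| 20% | about 11% too small | 23–24% too small |

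In SD units this runs from 0.07 × 0.333 = 0.02 to 0.24 × 0.467 = 0.11.

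**5. Difference gone or reversed by 6 h.** Change only the true 6 h difference. If it is 0, the answered-only estimate is −0.02 to −0.11 SD, a spurious difference. If it is −0.20 SD, the estimate is −0.22 to −0.31 SD, so a real difference is enlarged.

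**6. Non-answer that differs by arm.** On Section 10's scale (true difference 0.20), with loss depending on the compared rating itself, scenarios gave:
- 0.20 when loss is unrelated to pain, even at unequal rates of 10% and 30%;
- 0.18 when the same pain-related loss acts in both arms;
- 0.14 to 0.28 in several scenarios where the pattern of loss differs by arm.

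**7. Using the immediate rating.** Adjusting for it within each arm left a bias within about 0.002 SD in the scenarios of steps 4 and 5. The variance ratio is about 1 − r² × fraction missing. At 20% missing this is 1 − 0.25 × 0.2 = 0.95 or 1 − 0.49 × 0.2 = 0.90, a reduction of about 5 to 10%.

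**8. Size against sampling error.** The standard error in SD units is √(1/31 + 1/35) = 0.247 at 10% unreached and √(1/27 + 1/31) = 0.263 at 20%. The bias is then 0.02/0.247 to (0.15 × 0.467)/0.247, or about 0.1 to 0.3 standard errors, at 10%. At 20% it is (0.11 × 0.333)/0.263 to 0.11/0.263, or about 0.14 to 0.42.

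**The case against.** Four objections carry weight.

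- **Direction.** Because the study hypothesises no difference, a reader might infer that unreached patients always pull the result toward that hypothesis. The documents do not support this. It needs an early difference that persists with the same sign and non-answer that works alike in both arms. Section 1 places the lidocaine burning during the procedure, so a difference that fades or reverses by 6 h cannot be excluded. This objection stands in full.
- **The 24 h call.** A reader might infer that a patient missed at 6 h is dropped from Day 2. The three-call sentence is repeated there, which fits a rule applied to each call separately, and the word again may mean only the second scheduled call. What stands is that the text is ambiguous.
- **Exclusion is not stated.** Section 10 does not say that unreached patients are left out; it is silent. Leaving them out is the default result of comparing means, not a written rule.
- **Size.** The bias is under half a standard error even in the upper assumed cases, and those need a 7.4-fold change in odds per SD. This limits the weight of the point. It does not remove it, because the correction uses data already collected.

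**Conclusion.** The point holds as a cheap improvement. The follow-up rule is ambiguous, and one reading loses 24 h ratings for no gain. The only analysis described would by default use answered ratings alone at 6 h and 24 h, which can bias those comparisons if answering depends on immediate pain and the arms differ in it. The direction is not fixed.

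In the persisting-difference case the 6 h difference is about 7–15% too small at 10% unreached and 11–24% at 20%. These figures rest on the assumed correlation, strength of dependence and non-contact rates, none of which the documents supply. No 24 h scenario was run, so the concern there is qualitative. If answering is unrelated to pain there is no such bias. The immediate comparison is unaffected in any case.

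**What to change.** **Section 6.** State that a patient not reached after three attempts at about 6 h has a missing 6 h rating only, is still called at 24 h, and keeps the immediate rating in the analysis.

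**Section 10.** State that the 6 h and 24 h arm differences are estimated from one repeated-measures mixed model on all three ratings (arm, time, arm by time, unstructured covariance), including every randomised patient with at least one rating.

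**Cost.** Two sentences, one standard model and a few extra Day 2 calls to patients already in the study. The model assumes that missingness depends only on observed ratings, which is weaker than what the answered-only comparison assumes. It is therefore not guaranteed to correct loss driven by the unseen 6 h or 24 h pain itself. It also treats skewed 0–10 scores as roughly normal. The gain in precision is modest, about 5–10% of the variance at 20% missing, so it does not replace an allowance for unreached patients in the sample size.

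### Adverse events are picked up only passively: all three post-injection contacts script a pain score and nothing else, so a low event count would be hard to interpret

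*Combined protocol and SAP*

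**What the plan says.** Section 8 is a single sentence: "Adverse events will be reported to the IRB immediately through standard reporting mechanisms". It gives no definition of an adverse event, no method or window of collection, and no tabulation.

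Section 7 names what might occur. For the steroid, given in both arms, "the risks of a corticosteroid injection include hypopigmentation, skin atrophy, and hyperglycemia in patients with diabetes"; these are described as rare. For one arm only, "There is also a small risk of an allergic reaction to the lidocaine component". It adds that unknown or unanticipated effects are possible.

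Section 6 sets out three contacts after the injection:
- In clinic, straight after the injection, the scripted request is "Rate the injection experience on a scale of 0 to 10, 0 being no pain and 10 being the worst pain of your life".
- At about 6 hours, "a different study investigator will call the patient by phone to assess their current pain level with the visual analog scale". Section 6 says this caller does not know the treatment arm.
- On Day 2, "Approximately 24 hours after the injection, the study investigator will again call the patient by phone to assess their current pain level". At the end of this call patients are "encouraged to reach out to the principle investigator or clinic should any problems arise".

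No contact is scheduled after Day 2. Section 10 contains no safety analysis.

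**The concern.** Section 8 creates a reporting duty, but no procedure in Section 6 is designed to feed it. Staff who follow the scripts exactly will collect pain scores and will learn of other problems only if they happen to see one or the patient raises it.

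What is at stake is the meaning of the safety statement at the end of the trial. Part of the argument for the study, in Section 1, is that "lidocaine also adds cost and risk to the procedure"; Section 3 repeats the idea. A report of few or no adverse events will be read against that argument, yet it could mean either that little happened or that nobody asked. Data not collected in the calls cannot be recovered at analysis.

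**Working it through.** **1. Named risks against scheduled procedures.**

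| Risk (Section 7) | Arm | Asked about or looked for in Section 6? |
|---|---|---|
| Hypopigmentation | Both | No; after the clinic visit contact is by phone only |
| Skin atrophy | Both | No; same reason |
| Hyperglycemia in diabetics | Both | No; diabetes is recorded at entry but not linked to any later question |
| Allergic reaction to lidocaine | Lidocaine only | No scripted question; an early reaction could be seen in clinic |

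The enrolment target implies 73 × 2 = 146 planned calls, and none has a scripted safety question. Patients not reached on Day 2 after three attempts do not hear the invitation to report problems in that call.

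**2. The plan's own figure.** Section 10 gives a difference of 0.2, SD 0.3, 34 and 39 subjects, type I error 0.05 and power 0.8. The standardised difference is 0.2/0.3 = 0.667. A two-sided two-sample t-test with 1.1538 controls per experimental subject needs 33.9 and 39.1, and power at 34/39 is 0.800. The figure reproduces. It concerns pain only, and nothing in this point changes it.

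**3. What full collection with zero events would support.** The one-sided 95% upper limit is 1 − 0.05^(1/n):
- n = 73: 1 − 0.05^(1/73) = 4.0%
- n = 34: 1 − 0.05^(1/34) = 8.4%
- n = 39: 1 − 0.05^(1/39) = 7.4%

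These assume that every patient is followed and that the arms are exactly 34 and 39, which the coin flip in Section 5 does not guarantee. The 73 applies only to risks shared by both arms. No limit can be given for hyperglycemia, because the number of diabetic patients is not stated.

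**4. What incomplete capture does.** Suppose a fraction s of events comes to light; the documents give no value, so s is an assumption. Zero reports then bound only the product of s and the true rate, and the limit on the true rate is 4.0%/s:
- s = 1: 4.0%
- s = 0.5: 4.02%/0.5 = 8.0%
- s = 0.25: 4.02%/0.25 = 16.1%

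Under passive collection s is unknown, so no limit can be stated.

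**5. What the trial could show even with full collection.** For assumed true rates of 1%, 2% and 5% (not in the documents), the chance of at least one event in 73 patients, 1 − (1 − p)^73, is 52%, 77% and 98%. Seeing an isolated event is plausible. Comparing rare events between arms, with limits of 7% to 8% per arm, is not.

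**The case against.** The strongest defence has four parts.

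- **Other routes exist.** A physician injects and a co-investigator takes the rating, so an early reaction could be seen. Patients may volunteer problems in either call, and the Day 2 call invites later contact with no end date. Section 8 is not limited to answers given to the script. This stands. A reader might infer that the named risks would go uncounted in both arms, or that Sections 6 and 8 contradict each other. The documents support neither reading: ascertainment is passive, not absent, and lidocaine allergy can arise in one arm only.
- **The Day 1 gap may be covered elsewhere.** Section 6 says the consent form is gone through in depth on Day 1, and the consent pages are not available for review. They may tell patients whom to contact. This stands as a limit on the timing argument, but such an instruction would still be passive reporting.
- **Safety is not an objective.** The aim is pain, both treatments are described as standard care, and no safety claim is planned. This keeps the point from being critical. It does not remove the Section 8 duty or Section 7's allowance for unanticipated effects.
- **The sample is too small.** This stands too. The inability to compare rare risks is mainly a matter of sample size, and no change to the script cures it.

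**Conclusion.** The point holds as one of likely under-ascertainment. The three scripted questions ask only about pain, scheduled contact ends at about 24 hours, and nothing in the procedures actively seeks the events that Section 8 makes reportable. A low or zero count could not be interpreted, and even the 4.0% upper limit for 73 fully followed patients would be unavailable.

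It is tempting to add that most skin changes would be missed because they appear after 24 hours. The documents give no onset times, so that cannot be established from them. What can be said is that no later assessment is scheduled.

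The consequence is confined to safety reporting. The pain comparison is not affected. The change is worth making because it is cheap and the data cannot be obtained afterwards.

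**What to change.** Amend Section 6 as follows.

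(a) In each of the two existing calls, after the pain rating, the caller who is unaware of the arm asks one fixed question: has the patient had any problem since the injection, for example rash, itching, swelling or trouble breathing? Patients recorded as diabetic are also asked whether glucose readings have been higher than usual. Positive answers go to the principal investigator for Section 8 reporting, without the caller learning the arm. Add to Section 10 that events are listed descriptively by arm, with the number of patients asked at each call and no formal comparison.

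(b) Give the instruction to contact the investigator or clinic at the Day 1 visit as well, and keep it in the Day 2 call.

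(c) Optionally, record hypopigmentation or atrophy noted at any routine visit that falls before study conclusion. This must be done before identifiers are destroyed under Section 12, and late enrollees may have no such visit. State that later skin changes are otherwise not assessed.

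Cost: a short amendment, slightly longer calls, some minor events to record and, for (c), a chart check. No visit or procedure is added. Asking about pain first protects the rating within a call. There remains a small chance that the 6-hour symptom question colours the 24-hour pain rating, equally in both arms if blinding holds.
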